## 15. STATISTICAL METHODS AND CONSIDERATIONS

Prior to the analysis of the final study data, a detailed Statistical Analysis Plan (SAP) will be written describing all analyses that will be performed. The SAP will contain any modifications to the analysis plan described below.

### 15.1 Data Sets Analyzed

All eligible patients who are randomized into the study and receive at least one dose of the study drug (the Safety Population) will be included in the safety analysis.

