### 4. STUDY DESIGN

#### 4.1 Study Overview

The goal of the TLC Study is to evaluate the *feasibility, tolerability, acceptability and adherence* for lorcaserin among actively using, MSM with cocaine use disorders in a placebo-controlled 12-week trial. In a double-blind trial, 45 individuals will be randomly assigned (2:1) to receive 12 weeks of lorcaserin 20mg (n=30) or placebo (n=15), to be taken once a day.

Screening data will be reviewed to determine subject eligibility. Subjects who meet all inclusion criteria and none of the exclusion criteria will be entered into the study.

The following treatment regimens will be used:

- Experimental treatment: BELVIQ® XR (lorcaserin). 20 mg.
- Placebo or Comparator – Placebo, 20 mg.

Total duration of subject participation will be twelve weeks. Total duration of the study is expected to be 16 weeks.

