## **13. PROTOCOL VIOLATIONS**

A protocol violation occurs when the subject or investigator fails to adhere to significant protocol requirements affecting the inclusion, exclusion, subject safety and primary endpoint criteria. Protocol violations for this study include, but are not limited to, the following:

[figure not shown]
- Failure to meet inclusion/exclusion criteria
- Use of a prohibited concomitant medication (such as those listed in the exclusion criteria)

Failure to comply with Good Clinical Practice (GCP) guidelines will also result in a protocol violation. The PI will determine if a protocol violation will result in withdrawal of a subject.

When a protocol violation occurs, it will be discussed with the investigator and a Protocol Violation Form detailing the violation will be generated. This form will be signed by a Sponsor representative and the Investigator. A copy of the form will be filed in the site's regulatory binder and in the Sponsor's files.

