### 15.3 Analysis of Primary Endpoint

To establish the feasibility of enrolling and retaining 45 MSM with cocaine use disorder in a 12 week with 2:1 randomized, double-blind study of lorcaserin versus placebo. We will calculate the following feasibility measures: 1) proportion of those eligible among those screened; 2) proportion enrolled among those eligible; and 3) study completion rate. Process measures (e.g., visit length, counseling session completion) and reactions to study procedures will also be collected and reported. Between-group differences will be assessed using Fisher's exact and Wilcoxon rank sum tests. We will also calculate Kaplan-Meier curves for time to dropout, by group, and test for differences using the log-rank test. Precision: In the overall sample of 45, proportions will be estimated with margins of sampling error (MSEs; i.e., half widths of 95% confidence intervals) of  $\leq 14.4$  percentage points, and means with MSEs of 0.30 standard deviations, both typical for a small pilot study. While the study will only be powered to detect large between-group differences in process measures, it will provide warning of potential problems.

To explore the tolerability of lorcaserin versus placebo among MSM with cocaine use disorders, as determined by the number of adverse clinical events in the cocaine and placebo arms. We will compute the proportions of those experiencing adverse events, both overall and by type. Adverse clinical events, AEs and SAEs, and other binary safety outcomes will be presented as percent of participants that experience the safety outcome by treatment assignment. We will also classify AEs as any AE that results in stopping study medication, specific common AEs ( $>2\%$  in both groups), AEs for general organ system categories, and AEs potentially related to study drug. The probability of observing at least one AE with population incidence of 1, 2, and 5% in the active arm will be 26, 45, and 70% with 2:1 randomization, respectively.

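### Section 15.1 makes eligibility a condition of the Safety Population, so read literally it drops dosed participants who are later found ineligible from the safety analysis

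*Combined protocol and SAP*

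**What the plan says.** Section 15.1 consists of one sentence. It describes the Safety Population as "All eligible patients who are randomized into the study and receive at least one dose of the study drug" and says that these patients "will be included in the safety analysis". No other analysis set is defined there.

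Section 4.1 gives the intended entry rule: "Subjects who meet all inclusion criteria and none of the exclusion criteria will be entered into the study". Section 13 allows for that rule to be broken. Among its examples of protocol violations is "Failure to meet inclusion/exclusion criteria", and it adds: "The PI will determine if a protocol violation will result in withdrawal of a subject".

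Section 15.3 says that AEs, serious AEs and other binary safety outcomes "will be presented as percent of participants that experience the safety outcome by treatment assignment". Section 15.4 tabulates AEs by treatment group. Neither section restates or changes the population. The opening of Section 15 announces a later, detailed SAP that may modify the plan, but the text supplied contains no revised safety set.

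**The concern.** A safety set normally counts everyone exposed. Here a judgement about eligibility, which may be made after dosing and after an event, can decide whether a participant is counted.

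Late discovery is realistic. Some criteria depend on self-report or history (Section 6.2 item 2; Section 6.3 items 8 to 10). Under Section 14, clinicians check each other's charts and the DSMB's ongoing reviews cover subject eligibility.

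The stakes are more than formal. Tolerability is part of the primary objective (Section 3.1 and the synopsis). Section 2.2 says that safety in active cocaine users is not known, and Section 8.1 justifies the 2:1 allocation by better AE detection on lorcaserin. Several exclusion criteria in Section 6.3 concern safety, such as serotonergic medicines and severe liver or renal impairment. The people removed could therefore be those whose safety data matter most.

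**Working it through.** **Inputs.** Arm sizes are 30 and 15 (Section 4.1: "45 individuals will be randomly assigned (2:1) to receive 12 weeks of lorcaserin 20mg (n=30) or placebo (n=15"). The synopsis and Section 15.3 state the probability of at least one AE in the active arm as 26%, 45% and 70% at incidences of 1%, 2% and 5%. The number of ineligible dosed participants is not given, so 1 to 3 on lorcaserin is assumed. All 30 are assumed to be dosed.

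**Step 1: the plan's own figures.** The formula is P(at least one AE) = 1 − (1 − p)^n, with n = 30.
- p = 0.01: 1 − 0.99^30 = 26.0% (stated 26%; agrees)
- p = 0.02: 1 − 0.98^30 = 45.5% (stated 45%; agrees)
- p = 0.05: 1 − 0.95^30 = 78.5% (stated 70%; does not agree)

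The first two figures count every participant assigned to lorcaserin. The third is a separate discrepancy and is not a sign of a smaller safety set. A value of 70% at 5% incidence would need 23 or 24 participants (69.3% or 70.8%), but 24 participants would give only 21.4% and 38.4% at the two lower incidences.

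**Step 2: the same formula with participants dropped.**

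| Lorcaserin participants counted | 1% | 2% | 5% |
|---|---|---|---|
| 30 | 26.0% | 45.5% | 78.5% |
| 29 | 25.3% | 44.3% | 77.4% |
| 28 | 24.5% | 43.2% | 76.2% |
| 27 | 23.8% | 42.0% | 75.0% |

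At 2% and 5% incidence the loss is about 1 to 3.5 percentage points. At 1% it is smaller.

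**Step 3: observed counts.** Suppose that the only serious AE on lorcaserin occurs in a participant later found ineligible.
- Counted: 1/30 = 3.3% (exact 95% CI 0.1% to 17.2%).
- Dropped: 0/29 = 0% (exact 95% CI 0% to 11.9%).

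The event leaves the table. If the dropped person had no event and someone else did, 1/30 = 3.3% would become 1/29 = 3.4%. The direction therefore depends on who is dropped.

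**Step 4: the common-AE class.** Section 15.3 calls an AE common if it exceeds 2% in both groups. One participant is 1/30 = 3.3% of lorcaserin or 1/15 = 6.7% of placebo, so one person with the event puts an arm over the threshold. Removing that person can decide whether an AE type is classed as common.

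**The case against.** The strongest reply is that 'eligible' in this protocol is a screening status. Section 4.1 admits only people who meet all criteria, Section 8.1 speaks of eligible participants being randomized, and Section 15.3 takes the share enrolled among the eligible as a feasibility measure. On that usage, the word in 15.1 describes everyone who passed screening and removes nobody. Section 13 deals with violations and withdrawal, not with whose data are analysed. The detection figures at 1% and 2% match all 30 participants. Events in ineligible people would also stay visible elsewhere: the DSMB receives AE tables and individual serious AE reports (Section 14), and serious AEs go to the IRB regardless of causality (Section 17.2).

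Much of this stands. A reader might infer that the plan expressly orders such participants to be dropped. It does not: exclusion follows from one adjective, and another reading is open. A reader might also infer that AE rates will certainly be biased downward. The documents do not show that either, because some criteria, such as recent sexual behaviour or enrolment in another study, have no evident link to AE risk.

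The objection does not settle the wording. If the word means screening status, it adds nothing to randomization. If it means true eligibility, it removes exposed people. Section 15.1 does not say which is meant, and no other section returns a dosed, ineligible participant to the safety analysis. Reports to the DSMB and the IRB do not replace the final safety tables. The later SAP could resolve the point, but it would start from this definition.

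**Conclusion.** The point holds in conditional form. Taken literally, the only analysis set in the plan excludes dosed participants later found ineligible, and Section 13 shows that such participants can arise. Whether this was intended cannot be determined from the documents.

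The effect on detection probability is small: at 2% incidence, from 45.5% to between 44.3% and 42.0% if 1 to 3 of 30 are dropped. The effect on sparse counts can be decisive, since a lone serious event can disappear (1/30 to 0/29). Both results rest on assumed numbers of ineligible participants and on all 30 being dosed. Bias in AE rates is possible, and would be downward if violators are more prone to harm, but neither its presence nor its direction is established.

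**What to change.** Delete 'eligible' from Section 15.1, and carry the change into the SAP before the database is locked and the blind broken (Section 8.2). The Safety Population then comprises every randomized participant who takes one or more doses, whether or not an eligibility violation comes to light later. List the violators separately, with the criterion breached and any AEs, so that readers can judge their influence.

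Keep presentation by treatment assignment, as Section 15.3 states. Moving to treatment received would be a second change that conflicts with that text. It is not needed here and should be made only if the sponsor reconciles the two sections.

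The cost is a one-word deletion plus a listing, with no extra data collection. AE rates may look slightly less favourable. If the word was meant only as screening status, the deletion changes nothing in the analysis.

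The 70% figure at 5% incidence should be checked separately, since 30 participants give 78.5%.

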### 15.2 Demographic and Baseline Characteristics

The following demographic variables at screening will be summarized by treatment group: race, gender, age, educational attainment, employed, and HIV positivity.

### 15.3 Analysis of Primary Endpoint

To establish the feasibility of enrolling and retaining 45 MSM with cocaine use disorder in a 12 week with 2:1 randomized, double-blind study of lorcaserin versus placebo. We will calculate the following feasibility measures: 1) proportion of those eligible among those screened; 2) proportion enrolled among those eligible; and 3) study completion rate. Process measures (e.g., visit length, counseling session completion) and reactions to study procedures will also be collected and reported. Between-group differences will be assessed using Fisher's exact and Wilcoxon rank sum tests. We will also calculate Kaplan-Meier curves for time to dropout, by group, and test for differences using the log-rank test. Precision: In the overall sample of 45, proportions will be estimated with margins of sampling error (MSEs; i.e., half widths of 95% confidence intervals) of  $\leq 14.4$  percentage points, and means with MSEs of 0.30 standard deviations, both typical for a small pilot study. While the study will only be powered to detect large between-group differences in process measures, it will provide warning of potential problems.

To explore the tolerability of lorcaserin versus placebo among MSM with cocaine use disorders, as determined by the number of adverse clinical events in the cocaine and placebo arms. We will compute the proportions of those experiencing adverse events, both overall and by type. Adverse clinical events, AEs and SAEs, and other binary safety outcomes will be presented as percent of participants that experience the safety outcome by treatment assignment. We will also classify AEs as any AE that results in stopping study medication, specific common AEs ( $>2\%$  in both groups), AEs for general organ system categories, and AEs potentially related to study drug. The probability of observing at least one AE with population incidence of 1, 2, and 5% in the active arm will be 26, 45, and 70% with 2:1 randomization, respectively.

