TEST PRODUCT, DOSE, AND ROUTE OF ADMINISTRATION	BELVIQ® XR (lorcaserin) 20mg., manufactured by: Arena Pharmaceuticals: [name] Product will be administered orally each day for 12 weeks length of time.
CONTROL PRODUCT, DOSE AND ROUTE OF ADMINISTRATION	Placebo, 20 mg. Product will be administered orally each day for 12 weeks length of time.
DURATION OF SUBJECT PARTICIPATION AND DURATION OF STUDY	Subjects will be on study for up to 12 weeks Screening: up to 4 weeks Treatment: 12 weeks The total duration of the study is expected to be 16 weeks or 4 months. 1 month for subject recruitment and 3 months for treatment phase.
CONCOMITANT MEDICATIONS	Allowed: standard treatment  Prohibited: Serotonin reuptake inhibitors (SSRIs), selective serotonin-norepinephrine reuptake inhibitors (SNRIs), tricyclic antidepressants, monoamine oxidase inhibitors (MAOIs)
EFFICACY EVALUATIONS	
PRIMARY ENDPOINT	In the overall sample of 45, proportions will be estimated with margins of sampling error (MSEs; i.e., half widths of 95% confidence intervals) of $\leq$ 14.4 percentage points, and means with MSEs of 0.30 standard deviations, both typical for a small pilot study. While the study will only be powered to detect large between-group differences in process measures, it will provide warning of potential problems.
SECONDARY ENDPOINTS	We will also classify AEs as any AE that results in stopping study medication, specific common AEs ( $>2\%$ in both groups), AEs for general

	organ system categories, and AEs potentially related to study drug. The probability of observing at least one AE with population incidence of 1, 2, and 5% in the active arm will be 26, 45, and 70% with 2:1 randomization, respectively.
SAFETY EVALUATIONS	Change in clinical safety labs from baseline to Week 12 Incidence of adverse events
PLANNED INTERIM ANALYSES	No planned interim analyses

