STATISTICS Primary Analysis Plan	
To establish the feasibility of enrolling and retaining 45 MSM with cocaine use disorders in a 12-week 2:1 randomized, double-blind study of lorcaserin versus placebo. We will calculate the following feasibility measures: 1) proportion of those eligible among those screened; 2) proportion enrolled among those eligible; and 3) study completion rate. Process measures (e.g., visit length, counseling session completion) and reactions to study procedures will also be collected and reported. Between-group differences will be assessed using Fisher's exact and Wilcoxon rank sum tests. We will also calculate Kaplan-Meier curves for time to dropout, by group, and test for differences using the log-rank test. Precision: In the overall sample of 45, proportions will be estimated with margins of sampling error (MSEs; i.e., half widths of 95% confidence intervals) of <math>\leq 14.4</math> percentage points, and means with MSEs of 0.30 standard deviations, both typical for a small pilot study. While the study will only be powered to detect large between-group differences in process measures, it will provide warning of potential problems.
 
To explore the tolerability of lorcaserin versus placebo among MSM with cocaine use disorders, as determined by the number of adverse clinical events in the cocaine and placebo arms. We will compute the proportions of those experiencing adverse events, both overall and by type. Adverse clinical events, AEs and SAEs, and other binary safety outcomes will be presented as percent of participants that experience the safety outcome by treatment assignment. We will also classify AEs as any AE that results in stopping study medication, specific common AEs (<math>>2\%</math> in both groups), AEs for general organ system categories, and AEs potentially related to study drug. The probability of observing at least one AE with population incidence of 1, 2, and 5% in the active arm will be 26, 45, and 70% with 2:1 randomization, respectively.
 
To describe the acceptability and adherence for lorcaserin versus placebo MSM with cocaine use disorders. We will measure the acceptability of lorcaserin compared to placebo among participants through a qualitative interview and survey evaluations of the study procedures, study drug characteristics, and dosing schedule at the final visit. We will determine medication adherence via MEMs Cap data, pill count, and self-report from TLFB and SMS texts. Measures of interest will include percent of doses taken, patterns of adherence, and time to stopping medication. We will assess how these measures of adherence track with patterns of cocaine use as measured in TLFB and urinalysis. Concordance of the adherence measures will be examined using weighted Kappa and correlations.

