### 2.2 Risk / Benefit Assessment

**Lorcaserin is an FDA-approved medication that is well-tolerated with relatively few adverse events (AEs).** Three Phase 3 trials (cumulative N=7789) that evaluated lorcaserin's treatment effect on obesity have established its safety among patients with and without diabetes. The most

common reported side effects for lorcaserin include headaches, dizziness, fatigue, nausea, dry mouth, and constipation. In these trials, 8.6% of individuals given lorcaserin discontinued treatment as a result of AEs, compared to 6.7% individuals given placebo. Aside from pregnancy, there are no contraindications for lorcaserin. Nevertheless, the safety and tolerability of lorcaserin among active cocaine users is unknown. **Lorcaserin has a low potential for abuse.** The frequency of AEs associated with lorcaserin increases when taken above the therapeutic dose, which may limit abuse potential. A double-blind randomized crossover study to test abuse liability found that lorcaserin was similar to placebo with respect to subjective liking, overall liking, and ratings on desire to take the drug again. Exceeding the recommended lorcaserin dose levels (10 mg, twice daily) were associated with higher levels of known unpleasant side effects and subjective dislike, compared to placebo. Thus, lorcaserin dose escalation would result in primarily negative subjective effects; these self-regulating properties will likely limit the medication's abuse liability.

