## 8. STUDY TREATMENTS

### 8.1 Method of Assigning Subjects to Treatment Groups

Up to 45 eligible participants will be randomly assigned to lorcaserin or placebo treatment groups in a 2:1 allocation ratio (lorcaserin and placebo), using the computer-generated randomization code for the study blocks. Assignment of two-thirds of participants to the lorcaserin arm was specifically chosen to improve our ability to detect adverse events in the active treatment arm, while preserving our ability to assess recruitment in a study in which randomization to placebo is likely. The study biostatistician, Dr.

[name], will generate and provide the randomization code directly to the pharmacy. No study staff will have access to the code.

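### The 'common AE' rule (more than 2% in both groups) does not say how the groups are counted, and on none of the possible readings does it pick out common events

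*Combined protocol and SAP*

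**What the plan says.** Section 15.3, under the tolerability aim, lists four ways of classing AEs: those that lead to stopping study medication, specific common AEs, organ-system categories, and AEs potentially related to study drug. The second class is defined as more than 2% "in both groups), AEs for general organ system categories, and AEs potentially related to study drug". The synopsis repeats the rule in its Secondary Endpoints row ("in both groups), AEs for general") and in its Primary Analysis Plan row ("in both groups), AEs for general organ system categories"). None of the three places says how the percentage is formed or gives a minimum number of cases.

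The planned arms are 30 on lorcaserin and 15 on placebo (section 4.1). Section 8.1 sets a ceiling: "Up to 45 eligible participants will be randomly assigned to lorcaserin or placebo treatment groups". The safety analysis covers eligible randomized patients who "receive at least one dose of the study drug (the Safety Population" (section 15.1).

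Separately from this class, section 15.3 gives AE proportions overall, by type and by assigned treatment. Section 15.4 tabulates AEs by arm with patient counts, rates, severity and relationship to drug. Neither applies a frequency cut.

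**The concern.** A label for common events should bring forward the AEs that occur often enough to matter, particularly on active drug. This rule has two weaknesses. The word 'both', taken literally, requires the event to have occurred on placebo as well, so it turns away an event seen repeatedly on lorcaserin and never on placebo. The 2% figure is also very small for a trial of 45. If one case already passes it, the number does no filtering, and any selection comes from how 'both' is understood. At stake is whether one of the four stated AE classes tells the reader anything, and whether two analysts applying the text would produce the same list.

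**Working it through.** **Inputs.** n = 30 lorcaserin and 15 placebo (section 4.1), at most 45 in total (section 8.1). All randomized participants are assumed to take at least one dose, so the section 15.1 safety population equals the randomized one. The plan gives no AE rates by type for this population, so the true rates below are assumptions.

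**The plan's own figures.** No case count is stated for the 2% cut, so there is nothing to reproduce for the rule itself. The only AE calculation in section 15.3 is the chance of at least one event on lorcaserin, given as 26, 45 and 70% at incidences of 1, 2 and 5%. With n = 30, 1 − (1 − p)^30 gives 26.0%, 45.5% and 78.5%. The first two agree, which confirms the denominator of 30. The third does not agree, but that is a separate matter with no bearing on this point.

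**Step 1: what 2% means in cases.** One case is 1/30 = 3.3%, 1/15 = 6.7% and 1/45 = 2.2%. Two per cent of 30, 15 and 45 is 0.6, 0.3 and 0.9 of a participant. The smallest count above 2% is therefore 1 for each denominator. A smaller safety population only raises these percentages (1/42 = 2.4%). A cut of more than 2% first requires two cases when the denominator reaches 50 (1/50 = 2.0%, not above the cut), which exceeds the maximum enrolment.

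**Step 2: the rule on each reading.**
- Each arm separately: at least 1/30 and at least 1/15. An event with 0/15 on placebo fails whatever the lorcaserin count, even 30/30. So 8/30 v 0/15 is not common, and 1/30 v 1/15 is.
- Pooled, or either arm: at least one case anywhere. Every observed AE qualifies.

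**Step 3: chance of the label.** Let pL and pP be the true rates on lorcaserin and placebo.
- Per arm: [1 − (1 − pL)^30] × [1 − (1 − pP)^15]
- Pooled or either arm: 1 − (1 − pL)^30 × (1 − pP)^15
- At least 2 participants in either group: 1 − P(X_L ≤ 1) × P(X_P ≤ 1), with X_L and X_P binomial

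At 20% v 5%, for example, (0.80)^30 = 0.0012 and (0.95)^15 = 0.463. Per arm this gives 0.9988 × 0.537 = 0.536; pooled it gives 1 − 0.0012 × 0.463 = 0.999.

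| Assumed rates, lorcaserin v placebo | Per arm | Pooled or either arm | At least 2 in either group |
|---|---|---|---|
| 20% v 0% | 0% | 99.9% | 98.9% |
| 20% v 5% | 54% | 99.9% | 99.1% |
| 10% v 10% | 76% | 99.1% | 90% |
| 2% v 2% | 12% | 60% | 15% |

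The first row's 0% is true by construction. These are chances of receiving the label, not chances of being reported.

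**The case against.** The strongest reply is that nothing is lost. AEs appear by type and by arm under sections 15.3 and 15.4 without any frequency cut, so an event at 8/30 v 0/15 would be visible in those tables whatever label it carried. No test or decision uses the label. That stands, and it sets the severity.

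A second reply is that the harsher result depends on the per-arm reading. That also stands. The remark in section 15.3 about presenting results by assigned treatment concerns display and does not settle how the 2% is computed. On the pooled reading the label rate at 20% v 0% is already 99.9%. But the pooled reading does not rescue the rule, because it labels every observed event as common.

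A third reply is that section 15 announces a detailed SAP before final analysis: "The SAP will contain any modifications to the analysis plan described below". This is the natural place to settle the definition, but the rule as now written would still need changing there.

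A reader might go further and infer that the rule defeats the purpose of 2:1 allocation, which section 8.1 says "was specifically chosen to improve our ability to detect adverse events in the active treatment arm". The documents do not support that. Section 15.3 quantifies detection as the chance of observing at least one event, and the label does not change what is observed or recorded.

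**Conclusion.** The point holds at low severity. That the phrase is undefined and that the 2% cut lies below one case are both true on any reading. The exclusion of lorcaserin-only events holds only if the percentage is taken in each arm, which the text does not settle. On none of the readings does the class do its job: it either drops every event seen in one arm only or lists every event seen.

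The size depends on the assumed rates. At 20% on lorcaserin, the per-arm chance of the label rises from 0% to 54% as the placebo rate goes from 0% to 5%, against 99.9% pooled at both. So the reading matters most when the event is uncommon on placebo.

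A reader might infer that drug-specific harms would go unreported. They would not, given the tables in sections 15.3 and 15.4. This is a fault in one descriptive class, not a loss of safety data.

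**What to change.** In section 15.3, in both synopsis rows, and in the SAP still to be written, refer to either treatment group instead of both, and replace the 2% figure with a cut above one case. One workable example is at least 2 participants in either treatment group, with both arms' counts shown for each such event. Then 8/30 v 0/15 qualifies and 1/30 v 1/15 does not, and a count stays above one case if fewer than 45 are randomized. Settle it before unblinding, so that the definition is not chosen with arm results in view.

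The cost is one phrase and one number in three places, with no new data or procedures. Compared with the per-arm reading, slightly more rare events gain the label (15% against 12% at 2% v 2%). Because the arms are unequal, two participants is 2/30 = 6.7% of lorcaserin but 2/15 = 13.3% of placebo. At an equal true rate of 10%, lorcaserin alone reaches the cut 82% of the time (1 − 0.9^30 − 30 × 0.1 × 0.9^29) and placebo alone 45% (1 − 0.9^15 − 15 × 0.1 × 0.9^14). The SAP should therefore state that the label is not a comparison between arms. The figure of two is a choice; another cut above one case would also cure the fault.

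### The stated 70% chance of seeing at least one adverse event of 5% incidence in the active arm should be 79% with the planned 30 participants

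*Combined protocol and SAP*

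**What the plan says.** Section 4.1 sets the arm sizes: participants are randomized "to receive 12 weeks of lorcaserin 20mg (n=30) or placebo (n=15"). Section 8.1 gives the reason for the unequal allocation: placing two thirds of participants on lorcaserin "was specifically chosen to improve our ability to detect adverse events in the active treatment arm".

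Section 15.3 then puts numbers on that ability, as the chance that the trial sees "at least one AE with population incidence of 1, 2, and 5% in the active arm will be 26, 45, and 70" percent. The synopsis repeats the same three figures in its Secondary Endpoints row and again under Statistics, Primary Analysis Plan: "in the active arm will be 26, 45, and 70% with 2:1 randomization, respectively".

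Section 15.1 defines the denominator for safety. Eligible participants who are randomized and "receive at least one dose of the study drug (the Safety Population) will be included in the safety analysis".

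**The concern.** The three probabilities should come from one formula and one arm size, with only the incidence changing. The first two fit an arm of 30 and the third does not.

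This sentence is the plan's only quantification of adverse-event detection. Tolerability belongs to the primary objective (Section 3.1), and Section 2.2 says that the safety of lorcaserin in active cocaine users is not known. If some type of event is never seen on lorcaserin, a reader would turn to this sentence to judge what could have been missed. As written, it implies a 30% chance of missing an event of 5% incidence. The pilot is also meant to inform a larger trial (Section 2.1), so a wrong figure could be carried forward.

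**Working it through.** **Inputs**

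- Active-arm size n = 30 (Section 4.1 and the synopsis).
- Incidences p = 1%, 2% and 5%, with stated probabilities 26%, 45% and 70% (Section 15.3 and the synopsis).
- Safety denominator: everyone randomized and dosed at least once (Section 15.1), so later dropout does not reduce n.

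**Formula.** With independent participants, the probability that at least one of n has the event is 1 − (1 − p)^n.

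**Plan's figures at n = 30**

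| Incidence | Calculation | Result | Stated |
|---|---|---|---|
| 1% | 1 − 0.99^30 | 26.03% | 26% |
| 2% | 1 − 0.98^30 | 45.45% | 45% |
| 5% | 1 − 0.95^30 | 78.54% | 70% |

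The first two figures reproduce. The third is short by 78.5 − 70 = 8.5 percentage points. The probability of seeing no such event is 0.95^30 = 21.5%, against the 30% that the plan implies.

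**Could a different n explain it?** Solving n = ln(1 − stated) / ln(1 − p) for each figure gives:

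- 26% at 1%: n = 29.96
- 45% at 2%: n = 29.59
- 70% at 5%: n = 23.47

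Rounding to the nearest percent, n = 30 is the only whole number that gives 26% at 1%: n = 29 gives 25.28% and n = 31 gives 26.77%. It is also the only one that gives 45% at 2%: n = 29 gives 44.34% and n = 31 gives 46.54%. No whole number rounds to 70% at 5%: n = 23 gives 69.26% and n = 24 gives 70.80%. At n = 23 or 24 the first two figures would be about 21% and 37% to 38%.

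**Could a different method or denominator explain it?** For 5% incidence:

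| Variant | Result |
|---|---|
| Poisson, n = 30: 1 − exp(−1.5) | 77.7% |
| n = 28 (93% retention from Section 15.4, applied to 30) | 76.2% |
| Placebo arm, n = 15 | 53.7% |
| Whole sample, n = 45 | 90.1% |

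None comes within 2 points of 70%. The retention variant also moves the first two figures away from the text, to 24.5% and 43.2%.

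**The case against.** The strongest reply is that the mismatch shows the pair 5% and 70% to be wrong without showing which member is the slip. At n = 30 an incidence of 4% gives 70.61% (69.9% by Poisson). If decimals are cut instead of rounded, incidences of 1, 2 and 4% give exactly 26, 45 and 70. That is arithmetically sound, but the documents print 5% in all three places and nowhere give 4% for this calculation. At the incidence actually stated, 79% is right whatever the origin of the slip.

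The statements about a unique n do depend on rounding to the nearest percent. With truncation, n = 24 also gives 70% at 5%, and n = 31 also gives 26% at 1%. That does not rescue the sentence, because n = 24 gives 21.4% and 38.4% for the other two figures.

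Section 15.1 says who enters the safety analysis, not how these probabilities were calculated, and Section 8.1 makes 45 a ceiling on enrolment. So n = 30 is partly an inference. The 26% and 45% support it strongly.

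Finally, the consequence is small. The synopsis bases the number of subjects on margins of error, Section 8.1 argues for 2:1 without citing the 70%, and the planned safety analyses are percentages and tabulations by arm. A reader who relied on the 70% would be too cautious, not too reassured. All of this stands. It limits the importance of the error but does not make the figure correct.

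**Conclusion.** The concern holds. With 30 participants on lorcaserin, the probability of observing at least one adverse event of 5% incidence is 78.5%, not 70%, and the probability of missing it is 21.5%, not 30%. The figures for 1% and 2% are correct. The result assumes that all 30 planned participants are randomized and dosed, that participants are independent, and that the stated 5% incidence is the one intended. The error is conservative and leaves sample size, allocation and analyses untouched, but it misstates a design property tied to the primary tolerability objective.

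**What to change.** Change the third probability from 70% to 79%, so that the series reads 26, 45 and 79%, in Section 15.3 and in both synopsis rows (Secondary Endpoints; Statistics, Primary Analysis Plan). Add that the figures assume 30 participants in the active arm. When making the edit, the authors can confirm that 5% was the intended incidence. Section 15 provides for a detailed SAP before the final analysis, and the corrected figures should be carried into it. The cost is a text change in three places, with no effect on design, sample size or analysis.
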